6.3 Other Study Variables – Predictors and Independent Variables

There are many potential predictors for the effectiveness and safety of romiplostim. To further describe the effects of romiplostim therapy, the study will consider the following variables in study cohort establishment and analysis:

Variables considered in study cohort and patient strata establishment will include:

- Sex
- Age
- Race/ethnicity
- Body Mass Index (BMI) and/or Body Surface Index (BSI)
- Year of initial ITP diagnosis (1996 to 2000, 2001 to 2005, 2006 to 2010, 2010 to 2015, and 2016 to 2018)

- Country (the study will be conducted based upon the NHRS from each country, independent of the country considered)
- Adult chronic ITP disease condition: There are many factors that may affect the adult chronic ITP disease condition (eg, length of disease, severity, platelet counts, splenectomy, co-morbidity, and concurrent medication); therefore, a propensity score will be developed to establish the romiplostim Exposed Cohort and Unexposed Cohort for adult chronic ITP patients. The development of a propensity score is discussed in [Section 12.3](#).

Key variables considered in the analysis

- Demographic characteristics (eg, age and sex)
- BMI and/or BSI
- Disease conditions (eg, length of disease, severity, platelet counts, surgical procedure received, splenectomy, etc.)
- Propensity score (will be separated into 5 strata)
- Concurrent medication (eg, thrombopoietic agents)
- Surgical procedures (eg, splenectomy)
- Comorbidities (eg, infections, diabetes and disease or conditions that increase risk of thrombotic event)
- Medication durations and dosage

7. REGISTRY FOLLOW-UP PERIOD, EXPOSURE TIME, AND TIME AT RISK FROM EXPOSURE

7.1 Registry Follow-up Period

The follow-up period will be separated into 4 periods:

- Six months prior to receiving romiplostim therapy: This period is considered a cohort qualification and baseline establishment period. Using this period, the eligibility of subjects will be challenged and confirmed, disease conditions will be assessed, and propensity scores will be assigned for each patient. Based on the information, study cohorts will be established.

- Under treatment period: The period is defined as being from Index Date to 10 days after the last dose of romiplostim medication. During this period, all study outcomes will be assessed except for outcomes related to latency effects and post treatment effects.
- Period immediately after romiplostim treatment cessation: This period is defined as between 10 to 100 days after the last dosing. The period will be used to assess risk of worsened thrombocytopenia after treatment cessation (eg, platelet counts, bleeding, as well as rescue medication usage). As needed, this study will separate this time period into 2 sub-time periods: (3a) time period from 10 to 30 days after the last dose; and (3b) time period from 30 days to 100 days after the last dose.
- Post treatment period: This is defined as the period from 100 days after the last dosing to the end of the study. This period, as well as the aforementioned 3 periods, will be used to study long term effects of romiplostim (eg, malignancies).

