- A hypothetical concern regarding hematopoietic growth factors is that they may enhance the growth of existing malignancies or promote the growth of new malignancies that are influenced by the receptor-ligand axis. The TPO receptor is predominantly expressed on cells of the myeloid lineage, and there is no confirmed expression on solid tumors ([Graf et al, 1996](#); [Columbyova et al 1995](#)); therefore, it is not expected that romiplostim will promote the growth of solid tumors. In the ITP clinical program, there is no evidence of increased neoplasia, including hematopoietic malignancies; there is, however, a potential risk that TPO receptor agonists may stimulate the progression of existing hematopoietic malignancies or MDS among patients with thrombocytopenia caused by conditions other than ITP. Ongoing clinical studies in other patient populations, including MDS, will help to assess this potential risk.

Other potential risks include:

- Thrombotic/thromboembolic complications
- Progression of increased reticulin to an irreversible BM fibrotic state

In Europe, the product label includes further dose adjustment rules that have been specified by the European regulator as a risk minimization measure of thromboembolic risk and have not been tested in clinical trials.

Dose adjustment rules as specified in the European label

Platelet count (x 10 ⁹ /L)	Action
<50	Increase once weekly dose by 1 mcg/kg
>150 for 2 consecutive weeks ^a	Decrease once weekly dose by 1 mcg/kg
>250 ^a	Do not administer, continue to assess platelet count weekly After the platelet count has fallen to < 150 x 10 ⁹ /L, resume dosing with once weekly dose reduced by 1 µg/kg

^a Due to the inter-individual variable platelet response, in some patients platelet count may abruptly fall below 50 x 10⁹/L after dose reduction or treatment discontinuation. In these cases, if clinically appropriate, higher cut-off levels of platelet count for dose reduction (200 x 10⁹/L) and treatment interruption (400 x 10⁹/L) may be considered according to medical judgment

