7.2 Exposure Time

Exposure time is defined as the period the patient is receiving romiplostim therapy. A patient will be considered to be on “maintenance” therapy when the patient receives the same dose of romiplostim for 4 subsequent weeks.

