12.5 Description of Transient Worsened Thrombocytopenia After Romiplostim Treatment Cessation

The analysis will be conducted for the Exposed Cohort in chronic ITP patients.

The comparison will be based upon platelet counts among four predefined study time periods ([Section 7.1](#)).

- Comparison of mean (SD) platelet counts in four study time periods between study cohorts.
- Multiple regression to determine if the phenomenon of transient worsened thrombocytopenia exists after adjusting for other potential confounders and propensity scores. The propensity score-stratified analysis will also be used.

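### Section 7.1 anchors the treatment periods on one last dose per patient, so worsening after a discontinuation that is followed by a restart is filed as under treatment and missed by the cessation window

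*Protocol*

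**What the plan says.** Section 7.1 splits follow-up into four periods. After the six-month baseline comes the under-treatment period: "The period is defined as being from Index Date to 10 days after the last dose of romiplostim medication". Of the next period it says "This period is defined as between 10 to 100 days after the last dosing", with an optional split at day 30 into sub-periods 3a and 3b. Of the last it says "This is defined as the period from 100 days after the last dosing to the end of the study".

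The section also fixes what each period is for. Of the cessation window: "The period will be used to assess risk of worsened thrombocytopenia after treatment cessation". Of the under-treatment period: "During this period, all study outcomes will be assessed except for outcomes related to latency effects and post treatment effects".

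Section 7.2 adds "Exposure time is defined as the period the patient is receiving romiplostim therapy", with no rule for gaps. Section 12.5, which serves the secondary objective on worsened thrombocytopenia after cessation, states "The comparison will be based upon platelet counts among four predefined study time periods" and refers back to Section 7.1. Section 6.2 uses the same periods for average platelet counts and for clinically significant bleeding and rescue medication.

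**The concern.** Each patient has one index date and, on the plain reading, one last dose. Follow-up lasts up to 11 years (Section 3.1) and, according to the synopsis, continues after discontinuation, so any restart will be seen in the data. When one occurs, the last dose moves later and the earlier gap becomes under-treatment time.

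The cessation window is the only period assigned to worsening after stopping. If patients whose counts fall are more likely to be put back on treatment, whether an episode enters the window depends on its outcome, and the window under-represents the phenomenon it is meant to describe. The misfiled low counts also lower the under-treatment platelet mean, which narrows the contrast examined in Section 12.5. Bleeds and rescue use in the gap are credited to time under treatment.

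**Working it through.** The protocol states no figure that depends on this definition, so there is none to reproduce. The check has three parts.

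**1. The rule applied to one constructed patient.** Weekly doses on days 0 to 182, no drug until a restart on day 238 (a gap of 238 − 182 = 56 days), final dose on day 700. With one anchor, the under-treatment period ends on day 700 + 10 = 710 and the cessation window on day 700 + 100 = 800.

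| Day of platelet fall | Days since most recent dose | One last dose (Section 7.1) | Per course |
|---|---|---|---|
| 200 | 18 | under treatment | cessation (3a) |
| 215 | 33 | under treatment | cessation (3b) |
| 230 | 48 | under treatment | cessation (3b) |
| 720 | 20 | cessation | cessation |
| 850 | 150 | post-treatment | post-treatment |

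The two readings differ only in the gap before the restart. The cessation after the final dose is captured either way.

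**2. The same patient at successive data cuts.** Section 3.1 calls for annual reports with cumulative results.

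- Cut at day 230: the last dose so far is day 182, so day 200 is in the cessation window.
- Cut at day 365: the last dose so far is day 364, so day 200 is under treatment.
- Cut at day 730: the last dose is day 700, so day 200 is under treatment.

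One event changes period between reports although nothing about the event has changed.

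**3. Direction and possible size.** Let r be the true share of cessations with rebound (worsening after stopping), and a and b the probabilities of restart after rebound and after no rebound. Suppose restarters are still on drug at the cut and so contribute no window. The share seen in the window is then

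r(1 − a) / [r(1 − a) + (1 − r)(1 − b)].

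Equivalently, the true odds are multiplied by (1 − a)/(1 − b). The share is too low whenever a exceeds b and correct when a equals b. The protocol gives none of r, a or b, so all the values below are assumptions.

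| a / b | r = 10% | r = 20% | r = 30% | Rebound episodes kept (1 − a) |
|---|---|---|---|---|
| 30% / 30% | 10% | 20% | 30% | 70% |
| 30% / 10% | 8.0% | 16.3% | 25.0% | 70% |
| 50% / 10% | 5.8% | 12.2% | 19.2% | 50% |
| 80% / 10% | 2.4% | 5.3% | 8.7% | 20% |

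Example for r = 20%, a = 80%, b = 10%: 0.20 × 0.20 = 0.04; 0.80 × 0.90 = 0.72; 0.04 / 0.76 = 5.3%.

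**The case against.** The wording could be read per course. Section 7.1 does not spell out that the last dose means the final one in follow-up, and its third period could in principle be applied at each stop. An analysis plan that is not at hand might define episodes. This softens the point but does not remove it: a post-treatment period that runs to the end of the study fits only one final dose, and the protocol itself fixes these boundaries.

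A reader might infer that the cessation objective loses the very patients it concerns, or that the window keeps mainly those who no longer needed the drug. The documents do not support that. What is lost is episodes followed by a restart. Patients who rebound and stay off romiplostim, including those managed with rescue medication, remain in the window, and a restarter contributes the window after the final dose if follow-up allows.

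A reader might also take the label table in Section 2.3 as proof that patients rebound and restart. It is not. The hold described there is for high counts, and treating such a hold as time under treatment is reasonable. The footnote does say "in some patients platelet count may abruptly fall below 50 x 10⁹/L after dose reduction or treatment discontinuation", which makes post-cessation falls foreseeable, but it says nothing about restarting.

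The consequence is bounded as well. The objective is secondary and descriptive, and the primary bone marrow endpoint is untouched because time at risk in Section 7.3 runs from first exposure. On the other side, the optional Cox model with time-varying exposure (Section 12.4) is no remedy, since it leaves the four periods as they are.

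**Conclusion.** The point holds as a defect of definition. With one last dose per patient, events in a gap before a restart are placed in the wrong period and kept out of the analysis meant for them, and their placement can change between annual reports. This follows from the text and needs no assumed rate beyond some patients restarting.

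The downward bias in post-cessation worsening is conditional: it arises if rebound makes restart more likely. Its size is unknown. The range of 20% down to about 5% for a true 20% rests on assumed restart probabilities and on restarters contributing no window; it illustrates the mechanism and is not an estimate. The change is worth making because the objective is stated, the selection depends on the outcome, and the repair is cheap.

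**What to change.** Redefine the periods in Section 7.1 per treatment course, keeping the 10-, 30- and 100-day limits:

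- State an analytic gap length that counts as a discontinuation. It should exceed the 14-day interval left by one missed weekly dose; otherwise an isolated missed dose would open a cessation window.
- Once the gap is met, count the window from the last dose of that course. End it at day 100 or at the next dose, whichever comes first. A new dose reopens the under-treatment period.
- Keep doses withheld for high counts separate from discontinuations where the records or the platelet count allow.
- Report restart within the window as an outcome beside bleeding and rescue use.
- Allow for several windows per patient in the analysis, and apply the same classification at every annual cut.

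This is an analysis definition only and proposes no dosing rule.

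The cost is wording in Sections 7.1 and 12.5, slightly more programming, several windows per patient and shorter under-treatment time. Dosing records are needed in any case to find the last dose, and Sections 5.1 and 6.3 already foresee data on exposure, duration and dosage. Two limits remain. The protocol does not say that reasons for gaps are collected, so some holds may not be separable. A restart that comes sooner than the chosen gap will still count as under treatment, so the gap should be no longer than needed.

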3. PATIENT REGISTRY STUDY PLAN

3.1 Registry Design

The NCPRR is established on the basis of the NHRS of 3 Nordic countries: Denmark, Sweden, and Norway.

The study period will be between 01 January 2009 (starting date) and 31 December 2019 (ending date). Interim study reports will be developed for yearly submission to the Agency. Each annual report will describe include events occurring from 01 January through 31 December of the reporting period with cumulative results. All data sources will use the same cutoff date in calendar time, December 31st of the latest year for all data obtained from the NHRS databases. The patient experience (patient time) for all patients who receive at least 1 dose of romiplostim therapy will be included in the romiplostim exposure cohort after they receive romiplostim. The patient experience with ITP time before romiplostim exposure will be included in the romiplostim unexposed cohort, along with that for all adult chronic ITP patients who never receive romiplostim therapy during the study period.

Adult chronic ITP cohorts (romiplostim Exposed Cohort and Unexposed Cohort) include adult patients who are identified as having chronic ITP (incident and prevalent cases through both hospital discharge registry and outpatient clinic registry, as described by [Frederiksen and Schmidt, 1999](#)) on or after the starting date, and up to 1 year prior to the ending date. All patients will be followed-up for **at least 1 year and up to 11 years** in either of 2 cohorts: the romiplostim Exposed Cohort or Unexposed Cohort. Incident and recurrent outcomes of interest will be assessed on an annual basis.

All clinical outcomes (eg, thrombotic/thromboembolic events, hematological malignancies, and other potential outcomes of interest) will be identified by International Classification of Diseases – 10th Revision (ICD-10) codes from the NHRS databases (eg, hospital discharge registry, outpatient clinic registry, pathology registry, death registry, cancer registry, birth registry, and prescription registry) or by review of electronic medical records and/or paper medical charts. As needed, suspected and identified cases will be medically confirmed by review of electronic medical records and/or paper medical charts, laboratory testing results, BM biopsy reports, pathology data, pharmacy data, and other relevant health records. Laboratory data will be used to determine thrombocytosis and worsened thrombocytopenia after cessation of romiplostim.

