6.2 Outcomes

There are many outcomes in the NCPRR. They are:

Primary Outcome Endpoints:

- Incidence of increased BM reticulin and/or BM fibrosis with associated clinical signs⁴, confirmed by findings in BM biopsies among adult chronic ITP patients
- Incidence of reticulin and collagen BM fibrosis (reticulin fibrosis and collagen fibrosis: SNOMED codes: M49000, M49001, M49020, M99611) with associated clinical signs, confirmed by findings in a BM biopsy among adults chronic ITP patients

Secondary Endpoints:

Clinical Endpoints:

- Average platelet counts prior to, during, immediately after treatment cessation, and following romiplostim therapy (study periods are defined in [Section 7.1](#))
- Incidence of thrombocytosis (laboratory confirmation of a platelet count $> 450 \times 10^9/L$) with/without adverse events among adult chronic ITP patients
- Incidence of thrombotic/thromboembolic events (ICD-10: 180, 126)
- Incidence of hematological malignancies (focused on AML and MDS)
- Incidence of clinically significant bleeding and/or receipt of rescue ITP medications for each predefined romiplostim treatment period ([Section 7.1](#))
- Incidence of concurrent leukocytosis and anemia (measured by laboratory test results taken within 4 weeks of each other)
- Description of platelet counts and dose adjustment in mcg/kg of romiplostim in patients with cITP according to dose adjustment rules specified in the European SPC

⁴ Clinical signs: any of the following: splenomegaly, hepatomegaly, leukocytosis, and cytopenia.

BM Endpoints:

- Prevalence of reticulin and collagen fiber content in the first BM biopsies of adult chronic ITP patients prior to romiplostim therapy by splenectomy status
- Incidence of collagen fibrosis with associated clinical signs confirmed by findings in BM biopsies among adult chronic ITP patients
- Incidence of PMF (primary myelofibrosis) (ICD-10: c94.5) according to the WHO diagnostic criteria in adult chronic ITP patients who have BM data prior to and/or post romiplostim therapy
- Overall and specific incidence of BM fibrosis, including reticulin and collagen fiber content formation, and PMF among adult chronic ITP patients with BM data prior to and/or post romiplostim therapy
- Association between the aforementioned primary and secondary clinical outcomes and BM abnormal findings

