7.3 Time at Risk

Time at risk for the NCPRR is defined as from time after initial romiplostim exposure to occurrence of outcomes listed in [Section 6.2](#). For patients without these study outcomes, the time at risk will be from the index date to death, loss to follow-up, or the end of study, whichever comes first.

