12.4 Analysis for Long-term Effects

Analysis for long-term effects will be descriptive in nature. As the selection bias resulting from confounding by indication for this study could be very large, and as some impacts are not measurable, comparative analyses will be inherently challenging to interpret. For these reasons any comparative analyses must be considered as exploratory for signal detection and for the purpose of hypothesis generation. The incidence rates of clinically significant bleeding (inpatient and outpatient) and/or rescue medication use will be described for the Exposed Cohort and Unexposed Cohort:

- Kaplan-Meier survival curves will be constructed for patients with bleeding events for the Exposed Cohort and Unexposed Cohort.
- As needed, a Cox model with romiplostim exposure as a time-varying covariate will be used to compare the total event-free survival rates among exposed ITP patients and the unexposed cohort, with an estimation of the relative risk and associated 95% confidence interval. This analysis will adjust for potential confounders and propensity scores. Stratification by propensity score, significant year spans, and country may be considered for this analysis, although such an analysis will only be for exploratory and hypothesis generating purposes. Other treatment exposures,

health status, and disease conditions may also be considered for inclusion in the model as time-varying covariates.

Comparison of platelet counts in predefined time periods (prior to, during, immediately after treatment cessation, and post treatment) between the Exposed Cohort and Unexposed Cohort:

- Mean and SD
- As needed, a multiple regression will be used to test the difference between the Exposed Cohort and Unexposed Cohort. However, such an analysis will only be for exploratory and hypothesis-generating purposes.

Comparison of long-term safety (eg, thromboembolic risk, thrombocytosis, hematological malignancies, focused upon AML, and MDS), including:

- Description of rare and long latency events: Some events (eg, AML and MDS) are too few to conduct any meaningful statistical analysis or comparison. The study will provide detailed case descriptions for each case observed.
- Incidence rate of these events will be calculated.

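### Section 7.1 gives conflicting rules on whether AML, MDS and other long-latency outcomes are assessed while patients are on romiplostim

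*Protocol*

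**What the plan says.** Protocol Section 7.1 divides follow-up of romiplostim patients into four periods.

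- The first is pre-dose: "Six months prior to receiving romiplostim therapy: This period is considered a cohort qualification and baseline establishment period".
- The second is under treatment: "The period is defined as being from Index Date to 10 days after the last dose of romiplostim medication". Of this period the section says: "During this period, all study outcomes will be assessed except for outcomes related to latency effects and post treatment effects".
- The third runs from 10 to 100 days after the last dose. The fourth runs from day 100 to the end of the study.
- Of the fourth period the section says: "This period, as well as the aforementioned 3 periods, will be used to study long term effects of romiplostim (eg, malignancies".

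Section 7.1 does not define latency effects, but Section 12.4 shows which events are meant: "Description of rare and long latency events: Some events (eg, AML and MDS) are too few". Section 6.2 lists as a secondary endpoint "Incidence of hematological malignancies (focused on AML and MDS".

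Section 7.3 sets the denominator: "Time at risk for the NCPRR is defined as from time after initial romiplostim exposure to occurrence of outcomes listed in" Section 6.2. Section 3.1 allocates the time before the first dose: "The patient experience with ITP time before romiplostim exposure will be included in the romiplostim unexposed cohort".

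**The concern.** For one outcome and one period, Section 7.1 gives two instructions. The under-treatment bullet says that long-latency outcomes are not assessed from the first dose to 10 days after the last. The final bullet says that the same period is used for malignancies.

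The incidence of hematological malignancy and pre-malignant states in the exposed cohort is a stated secondary objective (Section 1.2). Section 2.3 names stimulation of existing hematopoietic malignancy or MDS as a potential risk of the drug class in thrombocytopenia from causes other than ITP. An analyst who followed the exclusion clause would remove on-treatment cases from the numerator and, under Section 7.3, keep the person-time. The error would run in the drug's favour. It would be largest in the longest users, who matter most for a long-term safety question.

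**Working it through.** **1. The passages side by side, for an AML or MDS diagnosed while the patient is on romiplostim**

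| Place | Instruction |
|---|---|
| 7.1, under-treatment bullet, read with 12.4 | Not assessed |
| 7.1, last bullet | Period is used for malignancies |
| 7.3, read with 6.2 | Patient is at risk, and the diagnosis ends the time at risk |
| 12.4 | Incidence rate is calculated, with no restriction by period |

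The first row conflicts with the other three. Nothing in the protocol ranks them.

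**2. Patients who never stop.** The under-treatment period ends 10 days after the last dose. A patient still dosing at the end of the study has no later period. Under the exclusion clause that patient adds person-time and can never add a case.

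**3. Size of the exposed cohort.** From the inputs in Section 3.5:

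- prevalent cases: 570 × 13 × 0.20 × 0.95 × 0.25 = 352.0
- incident cases: 570 × 10 × 0.20 × 0.95 × 0.25 = 270.75
- sum: 622.7, which reproduces the stated 623

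The 4,234 patient-years are taken as stated (4,234 / 623 = 6.8 years per patient).

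**4. Effect of following the exclusion clause.** Let r be the true yearly rate and s the on-treatment share of exposed person-time. With a constant rate:

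- expected cases = 4,234 × r
- cases dropped = 4,234 × r × s
- reported rate = r × (1 − s), so the rate is understated by the fraction s

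The protocol gives neither r nor s. Section 11 says that the background incidence is unknown. Both are assumed below.

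| Assumed r per year | Expected cases | Dropped, s = 20% | s = 40% | s = 60% | s = 80% |
|---|---|---|---|---|---|
| 0.1% | 4.2 | 0.8 | 1.7 | 2.5 | 3.4 |
| 0.2% | 8.5 | 1.7 | 3.4 | 5.1 | 6.8 |
| 0.5% | 21.2 | 4.2 | 8.5 | 12.7 | 16.9 |

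The relative understatement, 20% to 80%, does not depend on r.

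**5. The pre-dose six months.** This window holds at most 623 × 0.5 = 311.5 patient-years, and 311.5 / 4,234 = 7.4%. At 0.1%, 0.2% and 0.5% per year it yields 0.31, 0.62 and 1.56 expected cases. If all of these were added to the exposed numerator with the denominator unchanged, the exposed rate would rise by about 7.4%.

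**The case against.** The strongest reply is that the protocol read as a whole already counts on-treatment cases. The exclusion clause is general and names no outcome, whereas the last bullet names malignancies and covers the under-treatment period. Section 7.3 treats an AML as the event that ends time at risk, which makes little sense if it is not counted. The synopsis requires a narrative for every exposed patient who develops a hematologic malignancy, so no case would go unseen. The study is descriptive (Section 2.4), and Section 12.4 expects too few such events for meaningful comparison. All of this stands, and it lowers the severity. It does not remove the conflict: the exclusion clause is an explicit instruction, Section 12.4 places AML and MDS within it, and a narrative does not correct an incidence rate.

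A reader might go further and infer from the last bullet that pre-dose malignancies are pooled into the exposed rate, since the three earlier periods include the six months before the first dose. The documents do not support that. Section 3.1 assigns this time to the Unexposed Cohort, and Section 7.3 starts time at risk after first exposure. Using the pre-dose period to study long-term effects also fits the within-patient comparison in Section 3.4.1.

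It is true that the exclusion window in Section 3.4.2 is tied to the ITP diagnosis and not to the first dose. A patient with MDS found more than six months after the qualifying diagnosis, and before romiplostim, is therefore not excluded by it. That is a matter of eligibility and does not make the case an exposed event.

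Nor is a large effect to be expected from this source. One or two such cases could move a small count noticeably (1 / 8.5 = 12%; 2 / 4.2 = 48%), but the window is expected to hold only 0.3 to 0.6 cases at those rates.

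**Conclusion.** The contradiction in Section 7.1 is real and bears on a stated safety objective. Followed literally, the exclusion clause would understate the exposed AML/MDS rate by the on-treatment share of person-time. That is 20% to 80% if the share lies in that range, assuming a constant rate and an unchanged denominator. Patients who never stop would be unable to contribute a case.

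The plan does not pool pre-treatment cases into the exposed rate. Even on that reading the expected effect would be at most about 7%, assuming the same rate before and after the first dose. Here the wording needs only a clarification.

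Severity is moderate: the endpoint is secondary and descriptive, and the last bullet of Section 7.1, Section 7.3 and the required narratives all point towards counting on-treatment cases.

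**What to change.** Amend Section 7.1 as follows.

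- Delete the exclusion clause, or limit it to outcomes that can only arise after stopping. State which outcomes are meant by latency effects.
- State that AML, MDS, PMF and other long-latency outcomes are counted for the Exposed Cohort from the Index Date through the under-treatment, cessation and post-treatment periods, over the person-time in Section 7.3.
- State that the six pre-dose months serve only as baseline and for the separate pre-exposure comparison. Any event in them is counted in the Unexposed Cohort together with its person-time, as Section 3.1 requires, and not as an exposed event. Setting such events aside as baseline disease while leaving their person-time in the Unexposed Cohort would create a new mismatch of numerator and denominator.

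An analysis that lags exposure to allow for latency can be added as a sensitivity analysis. The cost is protocol wording, carried into the analysis plan; no new data are needed.
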